3. INTRODUCTION

3.1. Background

Chronic infection with hepatitis B virus (HBV) represents a major global public health problem. It is estimated by WHO that around 257 million people are living with HBV infection (defined as hepatitis B surface antigen positive) [WHO HBV Face Sheet]. Chronic HBV infection leads to an increased risk of cirrhosis, hepatic decompensation, hepatocellular carcinoma (HCC), and liver-related premature mortality. In 2015, HBV infection accounted for 887 000 deaths, mostly from complications (including cirrhosis and hepatocellular carcinoma) [WHO HBV Face Sheet]. HBV infection is particularly important in the Asian-Pacific region and China. More than one-third of the world's chronic HBV carriers live in China. It is estimated that over half a million of Chinese people die annually from end-stage liver diseases. HBV infection and progression to end-stage disease is also associated with significant economic burden to the healthcare system and the society. Successful prevention of HBV infection and disease progression will considerably reduce humanistic sufferings and socioeconomic burden [Sun, 2010].

Over the past decades, five oral nucleoside/nucleotide analogues (NUCs) have been approved for antiviral treatment of chronic hepatitis B (CHB) including Tenofovir Disoproxil Fumarate (TDF), Entecavir (ETV), Telbivudine (LdT), Adefovir (ADV) and Lamivudine (LAM). It has been established that the risk of disease progression is decreased through the sustained reduction in HBV deoxyribonucleic acid (DNA) to undetectable levels. NUCs have been shown to effectively reduce serum HBV DNA and alanine aminotransferase (ALT) levels and therefore improve patients' hepatic reserve and liver histology. For NUCs, lifetime treatment is suggested for Chronic Hepatitis B (CHB) patients with advanced liver disease or in some instances with chronic Immunosuppressive therapy. The generally favourable side-effect profiles of the five NUCs demonstrated in registration trials coupled with the low rates of antiviral drug resistance with the newer agents make them attractive for use beyond 1 year.

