8.2. Withdrawal from the Study

A participant may withdraw from the study at any time at his/her own request, or may be withdrawn at any time at the discretion of the investigator for safety, behavioral, compliance or administrative reasons. If the participant withdraws consent for disclosure of future information, the sponsor may retain and continue to use any data collected before such a withdrawal of consent.

In this real-world study, participants will be considered withdrawal from the study if any of the following events occurs within the 3-year study period:

Discontinuation of TDF (Viread, Beixin or Naxinde) for at least 28 days

Participation in clinical trials for any new drugs not limited to CHB-related ones during the 3-year study period

Study closed/terminated

Withdrew consent

The overall duration of TDF treatment and the reason for discontinuation of TDF treatment will be collected and the patient's adherence will be evaluated by the investigator a designed questionnaire.

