9.3.2. Primary Analyses

In order to evaluate the effectiveness of TDF for the treatment of CHB patients, the following estimates will be summarized for the overall analysis population and subpopulations (e.g. gender, age group, clinical characteristics).

- The proportion of patients who achieve CVR at week of 144
- The proportion of patients who achieve CVR at weeks of 48 and 96
- The proportion of patients who achieve HBeAg loss and/or HBeAg seroconversion in HBeAg positive patients at weeks of 48, 96, and 144
- The proportion of patients who achieve HBsAg loss and/or HBsAg seroconversion at weeks of 48, 96, and 144
- The proportion of patients who achieve transaminase normalization at weeks of 48, 96, and 144

Sub-groups are defined according to patients sociodemographic, lifestyle and clinical characteristics and on treatment factors, including age, gender, baseline HBV DNA level, HBeAg status, baseline alanine aminotransferase level in relation to the upper limit of the normal range, receipt or no-receipt of previous treatment with other NUCs, previous history of drug resistance, baseline genotype, comorbidities (cirrhosis, hypertension, diabetes, renal disease), patient treatment adherence.

A time window that ± 28 days for week 48, 96 and 144 will be applied in each cut-off analyses. As the supportive analyses, the analyses with time windows that ± 3 months will be conducted.

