9.3.5. Other Analyses

Missing data is inevitable in this real-world study and can have an impact upon the interpretation of the data. In general, values for missing data will not be imputed unless otherwise specified. As this study takes a naturalistic approach, there will be no protocoldictated interventions or approaches to improve patient compliance besides what physicians do in practice. The study will use innovative electronic data capture approaches to increase the efficiency of data collection and reduce the effort on patients, physicians and sites, hopefully to reduce the chance of missing data.

The duration of patients on TDF, the reason for discontinuation if possible, and patients' adherence will be evaluated and recorded. Missing data issue will be explored in data analyses. For example, the reason and occurrence time of missing data will be summarized. It might be informative to know more the missing data and improve the adherence of treatment in the future.

When applicable, additional analyses may be conducted on primary, secondary, and exploratory objectives and research questions and will be described in RAP.

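### HBeAg and HBsAg loss and seroconversion are counted only inside visit windows, so recorded events can drop out and the direction of the resulting error is not controlled

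*Protocol*

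**What the plan says.** Protocol section 9.3.2 lists among the primary analyses "The proportion of patients who achieve HBeAg loss and/or HBeAg seroconversion in HBeAg positive patients at weeks of 48, 96, and 144" and "The proportion of patients who achieve HBsAg loss and/or HBsAg seroconversion at weeks of 48, 96, and 144". The same section adds: "A time window that ± 28 days for week 48, 96 and 144 will be applied in each cut-off analyses". It then says: "As the supportive analyses, the analyses with time windows that ± 3 months will be conducted". No version of either endpoint counts events reached by a given week.

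Four other provisions decide who has a value in a window:

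- Section 8.2 counts as withdrawal "Discontinuation of TDF (Viread, Beixin or Naxinde) for at least 28 days", whatever the reason.
- Section 9.3.5 states that "values for missing data will not be imputed unless otherwise specified".
- Section 7 has no compulsory visits. It sends HBV DNA, eGFR and phosphate to the central laboratory and leaves other tests to local hospitals. Serology is therefore local and collected only if it was done.
- Section 9.3.4.2 plans Kaplan-Meier and Cox analysis for time to CVR only.

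Section 9.2 defines the main population by baseline data plus at least one later assessment. It gives no denominator for each time point.

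**The concern.** Loss of HBeAg or HBsAg is a milestone: the clinical question is usually whether, and by when, it was reached. Scoring it only from a test inside a 56-day window sets aside events already in the database. A patient with HBsAg loss recorded at month 18 who then stops TDF for 28 days has no week-96 or week-144 value. The same holds for a patient who stays on TDF but has no local serology in the later window.

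These are two of the four response endpoints listed in section 9.3.2. If the reported proportion reflects who was still tested as well as who responded, the week-144 figure is hard to interpret. It could even fall below the week-96 figure without any patient losing a response. Two analysts following the text could report different rates, depending on the denominator they chose.

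**Working it through.** **The plan's own figure.** Section 9.1.2 gives precision for CVR only. 1.96 × √(0.80 × 0.20 / 1300) = 0.0217, stated as 2.2%. For HBeAg-positive patients, 1.96 × √(0.16 / 708) = 0.0295, stated as 0.029. Both reproduce. No rate or precision is given for a serologic endpoint.

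**Do scheduled tests reach the windows?** Sections 2 and 7.3 set collection at 6-month intervals to month 36. Taking a month as 365.25/12 days and 3 months as 91 days:

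| Target | Main window (days) | Supportive window (days) | Scheduled month | Day | In main? | In supportive? |
|---|---|---|---|---|---|---|
| Week 48 (day 336) | 308–364 | 245–427 | 12 | 365 | No, by 1 day | Yes |
| Week 96 (day 672) | 644–700 | 581–763 | 24 | 730 | No, by about 30 days | Yes |
| Week 144 (day 1008) | 980–1036 | 917–1099 | 36 | 1096 | No, by about 60 days | Yes, by about 3 days |

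Months 6, 18 and 30 (days 183, 548 and 913) fall in no window of either width. On the nominal calendar schedule the main analysis receives no serology, and the supportive analysis uses three of six collections. Visits will scatter in practice, so some tests will fall inside. If sites read a month as four weeks, months 12, 24 and 36 coincide with the targets. The length of follow-up, 3 years, points to calendar months.

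**What missing values do to the rate.** Let π be the true cumulative proportion by week 144. Let r1 and r0 be the chances that a responder and a non-responder have a value in the window. Overall retention is held at 65%, from the 35% loss in section 9.1.2: π·r1 + (1−π)·r0 = 0.65.

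- Observed cases: π·r1 / 0.65.
- Missing counted as failure: π·r1.
- Ever achieved, over all analysed: π, provided that each event is recorded before the patient leaves.

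The document gives neither π nor r1. The values below are assumptions for illustration (observed-case rate, then missing-as-failure rate).

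| Endpoint, assumed π | r1 = 20% | r1 = 40% | r1 = 65% | r1 = 80% |
|---|---|---|---|---|
| HBsAg, 1% | 0.3%, 0.2% | 0.6%, 0.4% | 1.0%, 0.65% | 1.2%, 0.8% |
| HBsAg, 3% | 0.9%, 0.6% | 1.8%, 1.2% | 3.0%, 2.0% | 3.7%, 2.4% |
| HBeAg, 20% | 6.2%, 4% | 12.3%, 8% | 20.0%, 13% | 24.6%, 16% |
| HBeAg, 35% | 10.8%, 7% | 21.5%, 14% | 35.0%, 22.8% | 43.1%, 28% |

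Missing-as-failure is too low whenever r1 is below 1. The observed-case rate is too low if r1 < r0, right if they are equal, and too high if r1 > r0. Even where it is unbiased, responders go unused: with π = 20% of the 1090 HBeAg-positive patients (218) and r1 = 65%, 76 responders contribute nothing at week 144.

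**A trap in the remedy.** Counting every achiever while dropping lost non-responders overstates the rate. With π = 3% and r0 = 65%, 0.03 / (0.03 + 0.97 × 0.65) = 4.5%.

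**The case against.** A proportion at a time point in treated patients is a legitimate quantity. Section 9.3 leaves window detail to the reporting and analysis plan, and section 9.3.5 allows exceptions to the no-imputation rule. Section 9.3.4.2 also plans, if data permit, a mixed model for HBeAg outcomes. Much of this stands: nothing here is an outright error, and the later plan could add a cumulative definition. However, the protocol itself fixes the endpoints as windowed. The mixed model is exploratory, conditional on the data, and does not name HBsAg.

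A reader might infer more: that responders stop TDF because they responded, so that the rates are certainly biased downward. The documents do not support this. Section 3.1 says that "lifetime treatment is suggested for Chronic Hepatitis B (CHB) patients with advanced liver disease", or in some instances with immunosuppression. It does not say that others stop, or that a serologic response leads to stopping. Section 7.3 names lack of effect among its examples of reasons for discontinuation, which would remove non-responders.

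The arithmetic behind the stronger reading is also fragile. With an assumed 25% HBeAg seroconversion, removing 30% of responders and no one else gives 0.175 / 0.925 = 18.9%. If the same 30% goes missing within 35% overall loss, the result is 0.175 / 0.65 = 26.9%, above the true value. Nor can such shifts be set against the 2.9-point precision, which is for CVR at 80%. At 25% and n = 708 the half-width is 1.96 × √(0.25 × 0.75 / 708) = 3.2 points.

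**Conclusion.** The point holds as a weakness in how these endpoints are specified. Window scoring, the 28-day withdrawal rule, no default imputation and local, non-compulsory serology together let a documented responder have no value at later time points. Calendar-month tests at 12, 24 and 36 months also miss the main windows.

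The error can go either way. Rates are too low if missing patients stay in the denominator, or if responders leave or go untested more often. They are unbiased with observed cases and equal loss, and too high if non-responders leave more often. The size cannot be derived from the document: the figures above rest on assumed response and observation rates, with only the 35% loss taken from the protocol. A cumulative estimate is a worthwhile, low-cost improvement, not the repair of a demonstrated bias.

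**What to change.** In section 9.3.2, add the first documented event on TDF by weeks 48, 96 and 144, separately for:

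- HBeAg loss and HBeAg seroconversion, in patients HBeAg-positive at baseline;
- HBsAg loss and HBsAg seroconversion.

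Use all collected serology, whether or not it falls in a window, and keep achievers counted after they leave. Estimate by cumulative incidence over the whole analysis population, so that lost non-responders are not dropped from the denominator. Treat stopping TDF before response as a competing event. Keep the windowed proportion as supportive and state its denominator. Record serologic response reached as a reason for discontinuation; the present list is only of examples, so this adds a category without contradicting it.

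The cost is analysis wording and one form category; no visit or test is added. The downside is that a first-event measure does not show later sero-reversion, so report that as a separate count.

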- 1. Sociodemographic: a brief baseline survey will be administered to collect a minimal amount of information. Additional study relevant information (only for enrolled patients) will be collected to enable study analyses.
- 2. Laboratory assessments and other clinical assessments: patients will only be monitored according to their physicians' standard practice without additional study-specified interventions and evaluations. Only available assessments will be collected from routine testing/evaluations using electronic approaches.
- 3. Assessments may not be conducted at the exact scheduled time intervals as there will be no intervention for patients' clinical care. Only available assessments will be collected from routine testing/evaluations. The schedule is to remind physicians to collect data regularly.
- 4. Adverse event and pregnancy exposure reporting: only spontaneous AEs/SAEs and pregnancy exposure related to any GSK products will be reported and summarized.
- 5. The baseline assessment filling with grey colure is mandatory and requested for baseline data collection.
- 6. Follow-up data collection period (e.g. months 6, 12, 18, 24, 30, 36) for patients who have started TDF before the entry of study will be anchored to their actual TDF initiation dates.

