5. STUDY DESIGN

5.1. Overall Design

This is a China-based multi-center, prospective, longitudinal, real-world study, taking a naturalistic approach, capturing real-world medical practice and patient outcomes using a non-interventional design. Patients with diagnosed CHB who newly initiate and continue TDF monotherapy or combination therapy will be consecutively recruited from general and specialized hospitals across China. Site/hospital selection will consider geographic and hospital type/tier representativeness, investigators' research interest, as well as feasibility such as electronic data collection approaches. For non-enrolled subjects, reasons of exclusion will be collected.

During the study, patients will seek and receive medical care as they do in regular clinical practice setting without investigational product tested. Specifically, patients' diagnosis, treatment, and monitoring will be left to their physicians' routine practice without study-

dictated visits and procedures. Minimal patient evaluations will be done by physicians, e.g. baseline patient demographics and clinical characteristics and patients' treatment adherence. Minimal lab tests in line with routine clinical practice (HBV DNA, serum creatinine, and serum phosphate) will be conducted in a central lab on the basis of the judgement of treating physicians and willingness of patients.

Other patient data will be collected using electronic approaches, mainly from lab test reports or medical records at the entry of this study and thereafter at 6-month intervals for 3 years. As this is a real-world study without mandatory scheduled visits, patients may not seek medical care and conduct assessments (e.g. lab tests) exactly at 6-month intervals. The 6-month interval is set to remind investigators to collect data regularly.

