9.1.2. Sample Size Assumptions

Sample sizes are estimated based on feasibility and precision level achieved as no formal hypothesis will be tested in this study.

The primary objective of this study is to assess the effectiveness of TDF, with one important indicator being the proportion of subjects who achieve the CVR (i.e. HBV-DNA undetectable) at weeks of 48, 96, and 144. To be able to assess the CVR achievement at week 144, a sample size of 2,000 patients will provide a precision of no more than 2.2%, assuming the percentage of patients achieving CVR is 80% and the rate of loss-to-follow-up and discontinuation is 35%. The precision is calculated by the following: precision = $Z_{(1\alpha/2)}$ *SQRT(p*(1-p)/N), where Z is the critical value of normal distribution corresponding to the probability of 1- α /2 (corresponding to (1- α)*100% confidence interval), and p is the percentage of patients achieving CVR. It is half of the width of 95% confidence interval for the point estimate, which means that the lower and upper bounds of the 95% confidence interval for the patient proportion of interest will be within 2.2% of the point estimate (point estimate +/- 2.2%). In addition, there will be approximately a 73% probability of identifying a least one AE with a true AE rate of 0.1%.

For an exploratory purpose, more calculations about the precisions of evaluating the CVR achievement percentage are also provided for difference sub-populations, such as HBeAg positive or Cirrhosis. Assuming HBeAg positive (Cirrhosis) is made of 54.5% (20%) of HBV patients, the percentage of patients achieving CVR is 80% and 3 -year drop-out rate is 35%, a sample size of N=2000 will have 1090 (400) patients in the interested group and about 708 (260) completers and a precision of no more than 0.029 (0.049) [You, 2016].

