9.3. Statistical Analyses

A detailed Reporting and Analysis Plan (RAP) outlining details of data analyses will be created and described below. Besides the 144-week analysis, key analyses may be conducted annually with the 48-week and 96-week cut-off data to look at short-term patient outcomes. No adjustment for multiplicity will be made for these analyses.

Continuous variables will be summarized for overall population and various subgroups using mean (standard deviation) and/or median (range), while categorical variables will be summarized in tables of frequencies and percentages. Comparative analyses will be performed across sub-groups using Student's t test or analyses of variance for quantitative variables, and Pearson's Chi-square test (Fisher exact test might be used when necessary) for qualitative variables. Nonparametric tests will be used when necessary.

In primary and secondary analyses, as this is a real-world study without mandatory scheduled visits, the assessments (e.g. lab test) may not be conducted exactly at 6-month intervals, but to keep the robustness of the estimation for effectiveness and renal function change, a time window that ± 28 days for week 48, 96 and 144 will be applied in each cut-off analyses. As the supportive analyses, the analyses with time windows that ± 3 months will be conducted. More details will be included in Reporting and Analyses Plan (RAP).

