9.3.3. Secondary Analyses

Patients' renal functional change during TDF treatment period will be explored.

- The proportion of patients whose eGFR (MDRD equation) decline >20% from baseline at weeks of 48, 96 and up to week 144 will be summarized for the overall study analysis population and sub-group populations.
- Mean and 95% confidence intervals for the change from baseline in eGFR values will be calculated for the overall analysis population, as well as for the subpopulations of interests. A mixed effect model will be fitted to explore the impacts on the mean change from baseline in eGFR of fixed effects of age, gender, treatment-naïve or experienced, ADV or non-ADV, type of baseline comorbidities (Cirrhosis, Hypertension, diabetes mellitus (DM), non-overlapping), baseline eGFR values, baseline HBV-DNA counts, baseline HBeAg status, and other factors as appropriate, and random effects of subject ID.
- The percentage of change from baseline in eGFR will be estimated for the overall analysis population and by sub-populations at weeks 48, 96, and 144. Figures of mean eGFR values overall and the sub-populations of interests will be generated.
- The proportion of patients with confirmed a serum phosphate Grade 3 or 4 abnormality (<2.0 mg/dL) at weeks of 48, 98 and 144 will be summarized for the overall study analysis population and sub-group populations.
- The percentage of change from baseline in serum phosphate will be estimated for the overall analysis population and by sub-populations at weeks 48, 96, and 144. Figures of mean serum phosphate values overall and the sub-populations of interests will be generated.
- Mean and 95% confidence intervals for the change from baseline in serum phosphate values will be calculated for the overall analysis population, as well as for the sub-populations of interests. A mixed effect model will be fitted to explore the impacts on the mean change from baseline in serum phosphate of fixed effects of age, gender, treatment-naïve or experienced, ADV or non-ADV, type of baseline co-morbidities (Cirrhosis, Hypertension, DM, non-overlapping), baseline eGFR values, baseline HBV-DNA counts, baseline HBeAg status, baseline phosphorus and other factors as appropriate, and random effects of subject ID.

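### The primary ±28-day windows at weeks 48, 96 and 144 do not contain the month 12, 24 and 36 collection points; the gap is marginal at week 48, moderate at week 96 and serious at week 144

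*Protocol*

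**What the plan says.** **Collection calendar, in months.** Section 5.1 has data collected "at the entry of this study and thereafter at 6-month intervals for 3 years". The Schedule of Activities lists the same points, and its note 6 names them: "Follow-up data collection period (e.g. months 6, 12, 18, 24, 30, 36". Sections 2, 5.1 and 7 explain that these dates are reminders to investigators, that no visit is mandatory, and that tests may fall at other times.

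**Analysis calendar, in weeks.** Section 9.3, speaking of primary and secondary analyses, says "a time window that ± 28 days for week 48, 96 and 144 will be applied in each cut-off analyses". Section 9.3.2 repeats this for the primary estimates, "A time window that ± 28 days for week 48, 96 and 144 will be applied in each cut-off analyses", and adds: "As the supportive analyses, the analyses with time windows that ± 3 months will be conducted".

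**Missing values.** Section 9.3.5 says that in general "values for missing data will not be imputed unless otherwise specified".

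**Precision.** Section 9.1.2 says that for CVR at week 144 "a sample size of 2,000 patients will provide a precision of no more than 2.2" per cent, with CVR assumed at 80% and loss at 35%. Table 3 turns the 2,000 into 1,300 completers.

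**The concern.** Section 9.3 introduces the windows because tests may not fall exactly at 6-month intervals. A window chosen for that reason should surround the 6-month points. These windows are centred on multiples of 48 weeks, and a 48-week year is 29 days shorter than a calendar year, so the two calendars drift apart by about a month each year. By the third year the prompted assessment comes well after the window has closed.

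Two things are at stake. One is precision: an out-of-window value is missing for that time point and generally not imputed, so fewer than 1,300 patients would support the week-144 estimate. The other is selection: patients with an in-window value would tend to be those tested away from the prompted dates, possibly for clinical reasons. Week-144 CVR stands first among the primary estimates in Section 9.3.2, and the renal results at the same time points use the same window.

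**Working it through.** **1. The plan's own precision.** Inputs from Section 9.1.2: p = 0.80, N = 2,000, loss 35%. Evaluable n = 2,000 × 0.65 = 1,300. Half-width = 1.96 × √(0.80 × 0.20 / 1,300) = 0.0217, which reproduces the stated 0.022. It counts every completer as having a week-144 value.

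**2. Windows against collection points.** Baseline is day 0 and the window is 7 × week ± 28 days. Calendar months give days 365-366, 730-731 and 1095-1096, depending on leap years.

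| Time point | Window (days) | Prompted point | Day | Days after window closes |
|---|---|---|---|---|
| Week 48 | 308-364 | Month 12 | 365-366 | 1-2 |
| Week 96 | 644-700 | Month 24 | 730-731 | 30-31 |
| Week 144 | 980-1036 | Month 36 | 1095-1096 | 59-60 |

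Months 6 (days 181-184), 18 (546-550) and 30 (911-915) also lie in no primary window.

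**3. Month convention.** With 30-day months, month 12 is day 360 and falls inside. Month 24 (day 720) still misses by 20 days and month 36 (day 1080) by 44. Only 28-day months fit all three, and 36 × 28 = 1,008 days is 2.76 years, not 3.

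**4. Possible capture at week 144.** The protocol gives no distribution of test dates, so this is illustration. Assume each completer has one visit around month 30 (day 913.1) and one around month 36 (day 1095.75), independent and normal with the same SD. Days are whole, so the window limits are 979.5 and 1036.5. Capture = 1 − (1 − p30)(1 − p36).

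- SD 30 days: p36 = Φ(−1.975) − Φ(−3.875) = 0.024; p30 = 1 − Φ(2.21) = 0.013. Capture is 3.7%, n about 48, half-width 1.96 × √(0.16/48) = 0.113.
- SD 60 days: p36 = 0.135; p30 = 0.114. Capture = 1 − 0.865 × 0.886 = 23%, n about 305, half-width 0.045.
- Tests uniform in time, one per 6 months: 57/182.6 = 31%, n about 406, half-width 0.039.
- Tests uniform in time, one per 3 months: 57/91.3 = 62%, n about 811, half-width 0.028.

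**5. Earlier time points, nearest visit only, SD 30 days.** Week 48: Φ((364.5 − 365.25)/30) − Φ((307.5 − 365.25)/30) = 0.490 − 0.027 = 46%. Week 96: Φ((700.5 − 730.5)/30) − Φ((643.5 − 730.5)/30) = 0.159 − 0.002 = 16%.

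**6. Supportive window at week 144.** With 3 months as 91 days it runs from day 917 to 1099. At SD 30 days, p36 = Φ(0.125) = 0.550 and p30 = 1 − Φ(0.1125) = 0.455, so capture = 1 − 0.450 × 0.545 = 75%, n about 981, half-width 0.025. SD 15 to 60 days gives 75-76%. The result depends on how 3 months is defined: at 84 days the window ends on day 1092 and excludes month 36; at 90-92 days it ends on day 1098-1100 and includes it.

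**The case against.** The strongest reply is that the months are not visits. The protocol calls them reminders, and it cites guideline monitoring at least every 6 months, so 6 months is the longest recommended interval rather than the expected one. Patients tested more often have a fair chance of an in-window value. This stands: the real loss is unknown and may be much smaller than the scatter model suggests. It does not remove the mismatch, because the months are when investigators are prompted and the primary windows leave those dates out.

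Second, a reader might infer that the primary analysis will be nearly empty at all three time points. The documents do not support that. Zero capture applies only to exact attendance on calendar months. The week-48 miss is a day or two and vanishes with 30-day months, and nearly half of visits scattered around month 12 would still be captured. Counting only month-36 visits at week 144 gives about 2.4% and ±14 points at SD 30 days, but this overstates the loss because it omits the scheduled month-30 collection.

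Third, the ±3-month analysis is already planned, time to CVR is not tied to the windows, the mixed models are not stated to be restricted to in-window values, and no hypothesis is tested. All true, so the cost is precision and possible selection, not a failed test. But the wider window is only supportive.

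Fourth, the reporting and analysis plan may add detail. It cannot cure the point by following the protocol, which already fixes ±28 days for the primary and secondary analyses.

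**Conclusion.** The point holds. The protocol runs collection and analysis on two calendars and does not reconcile them. On calendar months no prompted assessment lies in any primary window. The gap is marginal at week 48 (1-2 days, dependent on convention), moderate at week 96 (about 30 days) and serious at week 144 (about 59 days).

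The effect on precision cannot be derived from the protocol. Under the assumed scatter, with months 30 and 36 both counted, the week-144 estimate would have a half-width between about ±11 points (SD 30 days) and ±4.5 points (SD 60 days). Uniform testing at 6-month spacing gives ±3.9 points, and more frequent testing comes nearer to the plan. The stated ±2.2 points is reached only if all 1,300 completers have an in-window value. The supportive window gives about ±2.5 points under the same scatter.

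The protocol also names week 98 for some endpoints, for example "<2.0 mg/dL) at weeks of 48, 98 and 144 will be summarized", while giving week 96 for related ones. That is a separate, minor and probably typographical inconsistency. It should be corrected but adds nothing to the window argument.

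**What to change.** Align the two calendars by one of two routes.

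- **Move the reminders.** Prompt collection at weeks 24, 48, 72, 96, 120 and 144 in Sections 2, 5.1 and 7. This keeps the stated endpoints and the number of prompts, and the last ±28-day window closes on day 1036, within 3 years. Tests remain at the discretion of the physician and patient.
- **Promote the wider window.** In Sections 9.3 and 9.3.2, make the already planned ±3-month window primary, define it in days (for example ±91, which gives non-overlapping windows), take the value closest to the target day, and keep ±28 days as sensitivity. The cost is a wider spread of actual test times around each nominal time point.

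Re-centring the windows on days 365, 730 and 1095 is less attractive: it redefines the week 48, 96 and 144 endpoints, and collecting to the end of the last window would run past the 3-year follow-up.

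With either route, restate the precision in Section 9.1.2 and Table 3 for the number of completers expected to have an in-window value. The change is to wording and reminder dates; no visits are added.
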